#### **Holding Study IO Interventions:**

When study interventions are administered in combination, if the AE is considered immune-related, all IO interventions should be held according to recommended dose modification criteria

If the toxicity does not resolve or the criteria for resuming treatment are not met, the participant must discontinue all IO therapy.

#### **Restarting Study Interventions:**

Participants may restart pembrolizumab and MT as described below.

- If the toxicities do resolve and conditions are aligned with what is defined in [Table 6], the study interventions may be restarted at the discretion of the investigator.

**Table 6 Dose modification and toxicity management guidelines for immune-related AEs associated with pembrolizumab and IO combination partners**

General instructions:				

 
1. Severe and life-threatening irAEs should be treated with IV corticosteroids followed by oral steroids. Other immunosuppressive treatment should begin if the irAEs are not controlled by corticosteroids.
 
2. All IO treatments must be permanently discontinued if the irAE does not resolve or the corticosteroid dose is not <math>\leq</math>10 mg/day within 12 weeks of the last study intervention treatment.
 
3. The corticosteroid taper should begin when the irAE is <math>\leq</math> Grade 1 and continue at least 4 weeks.
 
4. If IO treatments have been withheld, study intervention may resume after the irAE decreased to <math>\leq</math> Grade 1 after corticosteroid taper.
 
				

irAEs	Toxicity Grade (CTCAE v5.0)	Action With Pembrolizumab + all IO Drugs	Corticosteroid and/or Other Therapies	Monitoring and Follow-up
Pneumonitis	Grade 2	Withhold	
 
• Administer corticosteroids (initial dose of 1 to 2 mg/kg prednisone or equivalent) followed by taper
 
• Add prophylactic antibiotics for opportunistic infections
 
	
 
• Monitor participants for signs and symptoms of pneumonitis
 
• Evaluate participants with suspected pneumonitis with radiographic imaging and initiate corticosteroid treatment
 

	Recurrent Grade 2, Grade 3 or 4	Permanently discontinue		
Diarrhea/Colitis	Grade 2 or 3	Withhold	
 
• Administer corticosteroids (initial dose of 1 to 2 mg/kg prednisone or equivalent) followed by taper
 
	
 
• Monitor participants for signs and symptoms of enterocolitis (ie, diarrhea, abdominal pain, blood or mucus in stool with or without fever)
 

irAEs	Toxicity Grade (CTCAE v5.0)	Action With Pembrolizumab + all IO Drugs	Corticosteroid and/or Other Therapies	Monitoring and Follow-up
	Recurrent Grade 3 or Grade 4	Permanently discontinue		
and of bowel perforation (ie, peritoneal signs and ileus)
 
 
Participants with <math>\geq</math>Grade 2 diarrhea suspecting colitis should consider GI consultation and performing endoscopy to rule out colitis
 
Participants with diarrhea/colitis should be advised to drink liberal quantities of clear fluids. If sufficient oral fluid intake is not feasible, fluid and electrolytes should be substituted via IV infusion
 

AST or ALT Elevation or Increased Bilirubin	Grade 2 a	Withhold	
 
Administer corticosteroids (initial dose of 0.5 to 1 mg/kg prednisone or equivalent) followed by taper
 
	
 
Monitor with liver function tests (consider weekly or more frequently until liver enzyme value returned to baseline or is stable)
 

	Grade 3 b or 4 c	Permanently discontinue	
 
Administer corticosteroids (initial dose of 1 to 2 mg/kg prednisone or equivalent) followed by taper
 
	
T1DM or Hyperglycemia	New onset T1DM or Grade 3 or 4 hyperglycemia	Withhold d	
 
Initiate insulin replacement therapy for participants with T1DM
 
	
 
Monitor participants for hyperglycemia or other signs and symptoms of diabetes
 

irAEs	Toxicity Grade (CTCAE v5.0)	Action With Pembrolizumab + all IO Drugs	Corticosteroid and/or Other Therapies	Monitoring and Follow-up
	associated with evidence of $\beta$ -cell failure		
 
Administer antihyperglycemic in participants with hyperglycemia
 
	
Hypophysitis	Grade 2	Withhold	
 
Administer corticosteroids and initiate hormonal replacements as clinically indicated
 
	
 
Monitor for signs and symptoms of hypophysitis (including hypopituitarism and adrenal insufficiency)
 

	Grade 3 or 4	Withhold or permanently discontinue d		
Hyperthyroidism	Grade 2	Continue	
 
Treat with nonselective beta-blockers (eg, propranolol) or thionamides as appropriate
 
	
 
Monitor for signs and symptoms of thyroid disorders
 

	Grade 3 or 4	Withhold or permanently discontinue d		
Hypothyroidism	Grade 2, 3 or 4	Continue	
 
Initiate thyroid replacement hormones (eg, levothyroxine or liothyronine) per standard of care
 
	
 
Monitor for signs and symptoms of thyroid disorders
 

Nephritis: grading according to increased creatinine or acute kidney injury	Grade 2	Withhold	
 
Administer corticosteroids (prednisone 1 to 2 mg/kg or equivalent) followed by taper
 
	
 
Monitor changes of renal function
 

	Grade 3 or 4	Permanently discontinue		

irAEs	Toxicity Grade (CTCAE v5.0)	Action With Pembrolizumab + all IO Drugs	Corticosteroid and/or Other Therapies	Monitoring and Follow-up
Neurological Toxicities	Grade 2	Withhold	
 
Based on severity of AE administer corticosteroids
 
	
 
Ensure adequate evaluation to confirm etiology and/or exclude other causes
 

	Grade 3 or 4	Permanently discontinue		
Myocarditis	Asymptomatic cardiac enzyme elevation with clinical suspicion of myocarditis (previously CTCAE v4.0 Grade 1)	Withhold	
 
Based on severity of AE administer corticosteroids
 
	
 
Ensure adequate evaluation to confirm etiology and/or exclude other causes
 

	Grade 2, 3 or 4	Permanently discontinue		
Exfoliative Dermatologic Conditions	Suspected SJS, TEN, or DRESS	Withhold	
 
Based on severity of AE administer corticosteroids
 
	
 
Ensure adequate evaluation to confirm etiology or exclude other causes
 

	Confirmed SJS, TEN, or DRESS	Permanently discontinue		
All Other irAEs	Persistent Grade 2	Withhold	
 
Based on severity of AE administer corticosteroids
 
	
 
Ensure adequate evaluation to confirm etiology or exclude other causes
 

	Grade 3	Withhold or discontinue based on the event e		
	Recurrent Grade 3 or Grade 4	Permanently discontinue		

irAEs	Toxicity Grade (CTCAE v5.0)	Action With Pembrolizumab + all IO Drugs	Corticosteroid and/or Other Therapies	Monitoring and Follow-up

AE(s)=adverse event(s); ALT= alanine aminotransferase; AST=aspartate aminotransferase; CTCAE=Common Terminology Criteria for Adverse Events; DRESS=Drug Rash with Eosinophilia and Systemic Symptom; GI=gastrointestinal; IO=immuno-oncology; ir=immune related; IV=intravenous; SJS=Stevens-Johnson Syndrome; T1DM=type 1 diabetes mellitus; TEN=Toxic Epidermal Necrolysis; ULN=upper limit of normal.
				

Note: Non-irAE will be managed as appropriate, following clinical practice recommendations.
 
a AST/ALT: >3.0 to 5.0 x ULN if baseline normal; >3.0 to 5.0 x baseline, if baseline abnormal; bilirubin: >1.5 to 3.0 x ULN if baseline normal; >1.5 to 3.0 x baseline if baseline abnormal
 
b AST/ALT: >5.0 to 20.0 x ULN, if baseline normal; >5.0 to 20.0 x baseline, if baseline abnormal; bilirubin: >3.0 to 10.0 x ULN if baseline normal; >3.0 to 10.0 x baseline if baseline abnormal
 
c AST/ALT: >20.0 x ULN, if baseline normal; >20.0 x baseline, if baseline abnormal; bilirubin: >10.0 x ULN if baseline normal; >10.0 x baseline if baseline abnormal
 
d The decision to withhold or permanently discontinue pembrolizumab or its IO combination partner is at the discretion of the investigator or treating physician. If control achieved or <math>\leq</math> Grade 2, pembrolizumab or its IO combination partner may be resumed.
 
e Events that require discontinuation include but are not limited to: encephalitis and other clinically important irAEs (eg, vasculitis and sclerosing cholangitis).
				

CT**Table 7 Pembrolizumab Infusion Reaction Dose modification and Treatment Guidelines**

NCI CTCAE Grade	Treatment	Premedication at Subsequent Dosing
Grade 1 Mild reaction; infusion interruption not indicated; intervention not indicated	Increase monitoring of vital signs as medically indicated until the participant is deemed medically stable in the opinion of the investigator.	None
Grade 2 Requires therapy or infusion interruption but responds promptly to symptomatic treatment (e.g., antihistamines, NSAIDs, narcotics, IV fluids); prophylactic medications indicated for ≤24 hrs	
Stop Infusion.
 
Additional appropriate medical therapy may include but is not limited to:
 
IV fluids
 
Antihistamines
 
NSAIDs
 
Acetaminophen
 
Narcotics
 
Increase monitoring of vital signs as medically indicated until the participant is deemed medically stable in the opinion of the investigator. If symptoms resolve within 1 hour of stopping drug infusion, the infusion may be restarted at 50% of the original infusion rate (e.g. from 100 mL/hr to 50 mL/hr). Otherwise dosing will be held until symptoms resolve and the participant should be premedicated for the next scheduled dose.
 
Participants who develop Grade 2 toxicity despite adequate premedication should be permanently discontinued from further study drug intervention
	Participant may be premedicated 1.5h (± 30 minutes) prior to infusion of study intervention with: Diphenhydramine 50 mg po (or equivalent dose of antihistamine). Acetaminophen 500-1000 mg po (or equivalent dose of analgesic).
Grades 3 or 4 Grade 3: Prolonged (i.e., not rapidly responsive to symptomatic medication and/or brief interruption of infusion); recurrence of symptoms following initial improvement; hospitalization indicated for other clinical sequelae (e.g.,	
Stop Infusion.
 
Additional appropriate medical therapy may include but is not limited to:
 
Epinephrine**
 
IV fluids
 
Antihistamines
 
NSAIDs
 
Acetaminophen
 
Narcotics
 
Oxygen
 
Pressors
	No subsequent dosing

renal impairment, pulmonary infiltrates) Grade 4: Life-threatening; pressor or ventilatory support indicated	Corticosteroids Increase monitoring of vital signs as medically indicated until the participant is deemed medically stable in the opinion of the investigator. Hospitalization may be indicated. **In cases of anaphylaxis, epinephrine should be used immediately. Participant is permanently discontinued from further study drug intervention.	
Appropriate resuscitation equipment should be available at the bedside and a physician readily available during the period of drug administration. For further information, please refer to the Common Terminology Criteria for Adverse Events v5.0 (CTCAE) at http://ctep.cancer.gov		

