### Assessment of intensity/toxicity

- An event is defined as “serious” when it meets at least 1 of the predefined outcomes as described in the definition of an SAE, not when it is rated as severe.
- 1. The investigator will make an assessment of intensity for each AE and SAE (and other reportable safety event) according to the NCI Common Terminology for Adverse Events (CTCAE), version 5. Any AE that changes CTCAE grade over the course of a given episode will have each change of grade recorded on the AE CRFs/worksheets.
  - Grade 1: Mild; asymptomatic or mild symptoms; clinical or diagnostic observations only; intervention not indicated.
  - Grade 2: Moderate; minimal, local or noninvasive intervention indicated; limiting age-appropriate instrumental activities of daily living (ADL).
  - Grade 3: Severe or medically significant but not immediately life-threatening; hospitalization or prolongation of hospitalization indicated; disabling; limiting self-care ADL.
  - Grade 4: Life threatening consequences; urgent intervention indicated.
  - Grade 5: Death related to AE.

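### Table 6 sets a stricter restart threshold for grade 2 hypophysitis than for withheld grade 3-4 hypophysitis, and its restart criteria do not say how ongoing hormone replacement counts

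*Combined protocol and SAP*

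**What the plan says.** All of the restart rules are in Section 5.2.4, Table 6.

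- **Hypophysitis, grade 2:** withhold, with no footnote.
- **Hypophysitis, grade 3 or 4:** withhold or permanently discontinue, with footnote d.
- **Treatment, both rows:** "Administer corticosteroids and initiate hormonal replacements as clinically indicated".
- **General instruction 4 (default restart rule):** "If IO treatments have been withheld, study intervention may resume after the irAE decreased to" grade 1 or below, after the corticosteroid taper.
- **Footnote d:** the choice between withholding and stopping "is at the discretion of the investigator or treating physician. If control achieved or" the event is at most "Grade 2, pembrolizumab or its IO combination partner may be resumed".
- **General instruction 2 (permanent stop):** "All IO treatments must be permanently discontinued if the irAE does not resolve or the corticosteroid dose is not" at or below "10 mg/day within 12 weeks of the last study intervention treatment".

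Steroid replacement is accepted elsewhere in the protocol. Exclusion criterion 10 does not treat physiologic replacement for pituitary insufficiency as systemic treatment. Exclusion criterion 7 permits higher replacement doses on mitotane. Section 5.5.2 allows chronic replacement with mitotane, and Section 6.1.7.2 makes it part of mitotane care. None of these passages is linked to the Table 6 restart criteria.

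**The concern.** A restart rule normally asks at least as much after a severe event as after a moderate one. Here the grade threshold runs the other way. Two patients in the same final state can face different rules, and the one whose event was milder has to improve further before restarting.

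Footnote d joins its two conditions with an *or*. Read literally, a patient who had grade 3-4 hypophysitis and is now at grade 2 but still uncontrolled may be re-dosed.

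The second issue is how replacement counts. Hypophysitis can leave a continuing need for hormone replacement, which is the treatment the row prescribes. The table does not say whether such a patient has resolved or is at grade 1. It also does not say whether replacement glucocorticoid counts toward the 10 mg/day limit. In this trial that matters for patients with any immune-related event, because being on replacement steroid is expected with mitotane and is not in itself a sign of active immune toxicity.

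**Working it through.** No formula applies to the main point; the check is a comparison of the rules.

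**Step 1. Which rule governs each row.** The grade 2 row has no footnote d, so instruction 4 is the only restart threshold. The grade 3-4 row has footnote d, which contains its own restart sentence. If instruction 4 also bound grade 3-4 events, that sentence would have no effect. The workable reading is that the specific footnote displaces the general instruction.

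**Step 2. Apply the rules to patients.**

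| Peak grade | Current state | Rule | Restart allowed? |
|---|---|---|---|
| 2 | Grade 1, tapered | Instruction 4 | Yes |
| 2 | Grade 2 | Instruction 4 | No |
| 3-4, withheld | Grade 2, controlled | Footnote d | Yes |
| 3-4, withheld | Grade 2, not controlled | Footnote d (the *or*) | Yes |

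The second row against the third and fourth shows the inversion. The thresholds differ by one CTCAE grade (2 − 1 = 1), and only the severe row has the control route.

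**Step 3. Compare with the other endocrine rows.** Type 1 diabetes or hyperglycemia is withheld with footnote d. Grade 2 hyperthyroidism continues, and grade 3-4 carries footnote d. Hypothyroidism at grades 2 to 4 continues on thyroid replacement. Grade 2 hypophysitis is the only endocrine row that is withheld without footnote d.

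**Step 4. How replacement might be graded.** On the general scale in Appendix 5, grade 1 means "clinical or diagnostic observations only; intervention not indicated", while the next level reads "Grade 2: Moderate; minimal, local or noninvasive intervention indicated". A lasting need for replacement can therefore be read as grade 2, although nothing in Table 6 says that it must be.

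**Step 5. The instruction 2 clock.** Twelve weeks is 12 × 7 = 84 days, or 84 / 42 = 2 pembrolizumab cycles. Counting from the last pembrolizumab dose (an assumption, since mitotane is taken daily), an event found at the next dosing visit leaves 84 − 42 = 42 days to meet the limit. Instruction 2 has no grade exemption, so it covers both hypophysitis rows and every other immune-related event.

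**Step 6. Test the simplest repair.** Suppose footnote d were added to the grade 2 row. An event that never exceeded grade 2 already meets the condition of grade 2 or below on the day it is withheld, so the hold would have no effect. The two rows need a common rule based on control, not a copied footnote.

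**The case against.** **The overall path for severe events is not shown to be more lenient.** A reader might infer from the inversion that grade 3-4 hypophysitis is handled more loosely overall. The documents do not support that. The investigator may permanently discontinue after grade 3-4. The causality guidance in Appendix 5 also requires advance sponsor approval for rechallenge after a serious event that pembrolizumab may have caused. That control goes by seriousness, not grade, but the two overlap: grade 3 includes hospitalization being indicated, and hospitalization is a seriousness criterion. This stands and limits the claim to the restart threshold.

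**The protocol does deal with hormone replacement.** The hypophysitis rows order it, and four other places accept it. This also stands. Only the restart criteria and the 10 mg/day limit are silent on it.

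**A forced stop at 12 weeks needs a strict reading.** A reader might infer that a patient stable on replacement must come off pembrolizumab, losing up to 17 of 18 doses (18 − 1) after a first-dose event. That requires stable replacement to be graded 2 or called unresolved, or replacement steroid to count toward the limit. It also requires that the patient would otherwise have completed all 18 cycles. Table 6 grades by CTCAE v5.0, whose event-specific criteria are not in the documents, and instructions 1, 3 and 4 are about steroid given to treat the event. The strict reading is possible but not established. The missing prednisone-equivalent unit is minor, because other rows and exclusion criterion 7 use it.

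**An exemption for hypophysitis alone would be too narrow.** If replacement steroid counts under instruction 2, it counts equally for pneumonitis, colitis or nephritis in a patient on mitotane. This is correct, and the fix below follows it.

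**Conclusion.** The restart threshold for hypophysitis is inverted as written. This rests on taking footnote d as overriding instruction 4, the only reading that gives the footnote's restart sentence any effect. The restart criteria also leave open how continuing hormone replacement counts, and instruction 2 has no replacement exception in a trial where replacement steroid is part of background care.

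The size is small: one CTCAE grade plus the control route, affecting individual dosing decisions in probably very few of at most 50 patients. The documents give no hypophysitis rate, so no expected count is offered. A reader might also look for an effect on the monitoring rules. There is none: the toxicity definition in Section 7.0 is a separate counting rule, and no boundary, error rate, sample size or efficacy conclusion changes. This is a wording correction worth making at the next amendment.

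**What to change.** 1. **Add one note to both hypophysitis rows:** *If not permanently discontinued, pembrolizumab may resume once symptoms are controlled, on stable hormone replacement where needed, and steroid given to treat the event has been tapered. This takes precedence over instruction 4 and over the grade 2 threshold in footnote d.* Keep the discretion to discontinue after grade 3-4, and leave footnote d as it is for diabetes or hyperglycemia and for hyperthyroidism.
2. **Clarify instruction 2 for all immune-related events.** State that the limit is 10 mg/day prednisone equivalent of steroid given to treat the event, that physiologic or mitotane replacement does not count toward it, and that a need for hormone replacement alone is not an unresolved event.

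The cost is one table note and one amended instruction, with no added visits, tests or procedures. The grade 2 row becomes slightly more permissive, limited by the symptom-control condition. Some grade 3-4 restarts may be delayed, because being at grade 2 would no longer be enough without control and taper. The documents do not say whether a dose withheld for an immune-related event is given late or skipped, so that delay cannot be converted into missed doses.

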### **Other allowed dose interruption for pembrolizumab**

Pembrolizumab monotherapy or in combination may be interrupted for situations other than treatment-related AEs such as medical / surgical events and/or unforeseen circumstances not related to study intervention. However, intervention is to be restarted within 3 weeks of the originally scheduled dose and within 42 days of the previously administered dose, unless otherwise discussed with the Sponsor. The reason for study intervention interruption is to be documented in the patient's study record.

### **5.3 Randomization or Treatment Allocation**

N/A

### **5.4 Stratification**

N/A

### **5.5 Concomitant Medications/Vaccinations (allowed & prohibited)**

Medications or vaccinations specifically prohibited in the exclusion criteria are not allowed during the ongoing trial. If there is a clinical indication for one of these or other medications or vaccinations specifically prohibited during the trial, discontinuation from trial therapy or vaccination may be required. The final decision on any supportive therapy or vaccination rests with the investigator and/or the participant's primary physician. However, the decision to continue the participant on study intervention requires the mutual agreement of the investigator, the Sponsor, and the participant.

#### **5.5.1 Acceptable Concomitant Medications**

All treatments that the investigator considers necessary for a participant's welfare may be administered at the discretion of the investigator in keeping with the community standards of medical care. All concomitant medication will be recorded on the case report form (CRF) including all prescription, over-the-counter (OTC), herbal supplements, and IV medications and fluids. If changes occur during the trial period, documentation of drug dosage, frequency, route, and date may also be included on the CRF.

All concomitant medications received within 28 days prior to the first dose of trial intervention and up to 30 days after the last dose of trial intervention should be recorded. If participants experience an SAE or ECI, concomitant medications administered 30 days after the last dose of trial intervention are to be recorded as defined in Section 6.2.

### **5.5.2 Prohibited Concomitant Medications**

Participants are prohibited from receiving the following therapies during the Screening and Treatment Phase (including retreatment for post-complete response relapse) of this trial:

- Antineoplastic systemic chemotherapy or biological therapy
- Immunotherapy not specified in this protocol
- Chemotherapy not specified in this protocol
- Investigational agents other than pembrolizumab
- Radiation therapy is discouraged but radiation therapy to a symptomatic solitary lesion or to the brain may be allowed at the investigator's discretion,
- Live or attenuated vaccines within 30 days before the first dose of study intervention and while participating in the study.
- Systemic glucocorticoids except when used for the following purposes:
  - To modulate symptoms of an AE that is suspected to have an immunologic etiology
  - For the prevention of emesis
  - To premedicate for IV contrast allergies
  - To treat COPD exacerbations (only short-term oral or IV use in doses >10 mg/day prednisone equivalent)
  - For chronic systemic replacement while on MT therapy
- Other glucocorticoid use except when used for the following purposes:
  - For topical use or ocular use
  - Intraarticular joint use
  - For inhalation in the management of asthma or chronic obstructive pulmonary disease

Participants who, in the assessment by the investigator, require the use of any of the aforementioned treatments for clinical management should be removed from the study. All treatments that the Investigator considers necessary for a participant's welfare may be administered at the discretion of the Investigator in keeping with the community standards of medical care.

Medications or vaccinations specifically prohibited in the exclusion criteria are not allowed during the ongoing study. If there is a clinical indication for any medication or vaccination specifically prohibited

during the study, discontinuation from study therapy or vaccination may be required. The final decision on any supportive therapy or vaccination rests with the investigator and/or the participant's primary physician. However, the decision to continue the participant on study treatment requires the mutual agreement of the investigator, the Sponsor and the participant. However, the decision to continue the participant on study intervention requires the mutual agreement of the investigator, the Sponsor, and the participant.

There are no prohibited therapies during the Post-Treatment Follow-up Phase.

